Methods: Approximately 42 patients, between the ages of 18-65 years, will be consecutively recruited to participate in a randomized prospective clinical trial. Enrolled subjects will be randomly allocated into one of 3 groups: Standard Invisalign therapy (G1-control), Accelerated Invisalign therapy + vibration (G2) and Accelerated Invisalign therapy without vibration (G3). Data collection will include intra oral scans of both the maxillary and mandibular dentition at 5 different time points: TO (baseline), T1 (4 days), T2 (14 days), T3 (6 weeks) and T4 (12 weeks). In addition, PerioPaper strips will be used to sample gingival crevicular fluid at each of the time points listed above. Research subjects will also be asked to complete a daily diary regarding their pain level during treatment. Data analysis will be used to specifically evaluate alignment of adjacent teeth and translational, and/or rotational, tooth movement will be evaluated by superimposing digital models recorded at the specific time points. Inflammation biomarkers will be analyzed with ELISA. Finally, the

statistical significance of our data will be evaluated with a 3 way repeated ANOVA as well as a post hoc comparison with Bonferri correction. P values less than .05 will be considered statistically significant.

Specific Aims:

In this study, we propose a randomized prospective clinical design to investigate effects of vibration therapy, using an AcceleDent Aura® device, on the rate of orthodontic tooth movement, activation of gingival crevicular fluid inflammation biomarkers and patient discomfort in conjunction with accelerated Invisalign therapy.

Hypothesis:

We propose vibration therapy will accelerate orthodontic tooth movement, increase inflammation biomarkers and reduce pain for orthodontic patients.

Background:

Align Technology©, Inc. developed Invisalign® in 1997 to meet the esthetic demands of orthodontic patients and providers. Invisalign patients receive a series of computer-assisted designed stereolithic clear retainers to incrementally resolve their malocclusion. Invisalign® and other advances in orthodontic technology such as clear aligners, ceramic brackets and lingual braces offer options to address the esthetic demands of most orthodontic patients but duration of treatment continues to be one of the most challenging aspects of practice.²

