 - a. In this study, we propose a single-blinded (Invisalign faculty) randomized prospective paralleled clinical trial to investigate effects of AcceleDent vibration therapy on the efficiency of tooth movement, on the activation of gingival crevicular fluid biomarkers and on patient discomfort in conjunction with accelerated Invisalign therapy. Enrolled subjects will be randomly allocated into one of 3 groups: Standard Invisalign therapy (G1-control), Accelerated Invisalign therapy + vibration (G2) and Accelerated Invisalign therapy without vibration (G3). Patients allocated to the standard Invisalign group will change aligners every 2

weeks while the both intervention groups will change aligners every 4 days. Patients allocated to the vibration group will receive an AcceleDent Aura device and bite down on the mouthpiece for 20 minutes/day. The AcceleDent Aura device vibrates at a .25N (25 grams) force level with a 30 Hz frequency. Data collection will include intra oral scans of both the maxillary and mandibular dentition at 5 different time points: TO (baseline), T1 (4 days), T2 (14 days), T3 (6 weeks) and T4 (12 weeks). In addition, PerioPaper strips will be used to sample gingival crevicular fluid at each of the time points listed above. Research subjects will also be asked to complete a daily diary regarding their pain level during treatment. Treatment plans for enrolled patients will be created using Invisalign's proprietary software: Clincheck Pro®. To reduce treatment plan variability and reduce potential sources of error, [name], who is an "Elite Top 1% Invisalign provider" and also a member of the exclusive North American Invisalign Clinical Advisory Board, will approve each treatment plan. [name] will also be blinded to any patients participation within the study in order to eliminate potential bias.

2. Recruitment:

- a. Participants will be conveniently recruited from the sample population of individuals seeking Invisalign orthodontic therapy within the UNC Graduate Orthodontic Clinic. Benefits for participants will include complementary vibration therapy using the AcceleDent Aura device, which is an estimated value of \$800. Financial reimbursement will also be offered to offset any parking fees associated with the study.
- 3. Power Analysis:

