 - a. Our study will have 3 groups for evaluation: G1 control (Invisalign on a 2week aligner schedule) and 2 intervention groups, G2 and G3 (each on an accelerated 4 days aligner schedule). The only difference between the intervention groups will be the use of vibration (G2 with vibration vs G3 without vibration). The expected rate of tooth movement for G1 will be .04mm/day (.25mm/week or .5mm/2 weeks) while the expected rate of tooth movement for G2 and G3 will be .28mm/day (.5mm in 4 days). The standard deviation is assumed 0.1 for three groups. Based on our sample calculation to achieve an adequate power, we will attempt to recruit a total of 42 patients to account for a dropout rate of 30%. Ideally, we would like to have a total sample size of 21 patients to ensure each of 3 study groups will have 7 patients, which will achieve more than 0.8 power even under a Bonferroni correction for multiple comparisons.
- 4. Randomization:
 - a. Our patients will be randomly allocated into the 3 groups based on a block randomization with size 6. The list will be independently generated by our study biostatistician.
- 5. Type I error and statistical significance:
 - a. P values less than .05 will be considered statistically significant in the overall test
- 6. Inclusion Criteria:
 - a. Males or females over the age of 18 years old desiring orthodontic treatment.

- b. Adult dentition with all upper and lower front teeth present and any premolar and molar combination in the upper posterior of two teeth on each side.
- c. Normal pulp vitality and healthy periodontal tissues as determined by intraoral exam.
- d. Good health as determined by medical history.
- e. Willingness and ability to comply with study procedures, attend study visits, and complete the study.
- f. The ability to understand and sign a written informed consent form, which must be signed prior to initiation of study procedures.
- 7. Exclusion Criteria:
 - a. Patient under the age of 18 years old
 - b. Patients diagnosed with systemic diseases such as diabetes, hypertension (high blood pressure), temporomandibular disorders (jaw disorders), or craniofacial syndromes.
 - c. Severe malocclusions that would require adjunctive procedures other than Invisalign. These include impacted teeth, closure of extractions spaces.
 - d. Significant periodontal disease (> 4mm pocket depth or >2 mm of recession on upper anterior teeth).
 - e. Active caries not under care of either a dentist or periodontist.

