 - f. Chronic daily use of any non-steroidal anti-inflammatory medication, estrogen, calcitonin, or corticosteroids.
 - **g.** History of use or current use of any bisphosphonate medication or other medication for treatment of osteoporosis.
 - h. Current smoker (must not have smoked in the last 6 months).
 - i. Failing to comply with research protocols
- 8. Arms:
 - a. Control Group (G1): 14 patients, standard Invisalign therapy with 2 week aligner schedule
 - a. Intervention Group (G2): 14 patients, accelerated Invisalign + vibration
 i. AcceleDent device 20 minutes/day per manufacturer's instructions

b. Intervention Group (G3): 14 patients, accelerated Invisalign + no vibration

- 7. Clinical Trial Protocol:
 - a. Visit #1: Clinical Screening with UNC Orthodontic Faculty (clinical purposes only)
 - i. Brief discussion of findings with patient and eligibility for Invisalign
 - b. Visit #2: Clinical exam and records (clinical purposes only), 30 days post visit #1
 - i. Completion of medical history
 - ii. Completion of extra and intra oral exams
 - iii. Completion of alginate impressions
 - iv. Photographs (extra and intra oral)
 - v. Xrays- Panoramic and Cephalometric
 - c. Visit #3: Treatment Plan Presentation (Experimental Baseline), 60 days post visit #1

- i. Clinical Procedures:
 - 1. Treatment plan presentation
 - a. Each treatment plan will be approved by [name] who will be blinded to a patient's study participation
 - 2. Invisalign impressions with PVS material
- ii. Research Procedures:
 - 1. Study recruitment
 - 2. Informed Consent
 - 3. iTero intraoral scan
 - 4. Completion of the Inclusion/Exclusion Case Report Form
- d. Visit #4: (120 days post visit #1/Day #1 of active treatment)
 - i. Clinical Procedures:
 - 1. Intraoral exam and intraoral photographs
 - 2. Deliver aligner number 1 and usage instructions
 - ii. Research Procedures:
 - 1. Deliver AcceleDent Aura device along with instructions
 - 2. Collection of gingival crevicular fluid biomarkers
 - 3. Completion of Faces Pain Scale
 - 4. Deliver daily diaries
- e. Visit #5: (125 days post visit #1/ Day #5 of active treatment)
 - i. Clinical procedures:
 - 1. Deliver aligners 2-4 to accelerate Invisalign groups and aligner schedule instructions
 - ii. Research Procedures:
 - 1. iTero intraoral scan
 - 2. Collection of gingival crevicular fluid biomarkers
 - 3. Completion of Faces Pain Scale and Adverse Event Form
- f. Visit #6: (134 days post visit #1/Day #14 of active treatment)

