 - a. Patients who experience an adverse event or reaction such as: uncontrolled pain or allergy will be disenrolled from the study and allowed to continue Invisalign therapy using the standard two-week aligner schedule. In addition, non-compliant patients will be disenrolled from the study and recommend to continue Invisalign therapy using the standard protocol.
- 10. Data Analysis:
 - a. Tooth leveling and alignment
 - i. Little's Index
 - b. Tooth rotations and translations
 - i. Euler's Law of Motion (6 degrees of freedom)
 - ii. 3D surface mapping
 - c. Alternative measurement options
 - i. Screw Method
 - d. Inflammation biomarkers within gingival crevicular fluid
 - i. ELISA
 - e. Orthodontic Pain Assessment
 - i. Faces Pain Scale
- 11. Statistical Analysis:
 - a. In order to complete statistical analysis for maxillary and mandibular dentition, we will compare the five time points within each group as well as the three groups across each time point.
 - b. Our primary statistical method will be a three-way repeated measurement ANOVA, with the main effects being: vibration, aligner schedule, and time. The ANOVA measurement will identify significant differences within the data and the post hoc comparison will determine which specific variables are involved. In order for a relationship to be considered statistically significant, the p-value must be less than .05.
 - c. One additional method for statistical analysis could be a survival analysis which would be more favorable in the case our study experiences a high volume of drop-outs during treatment.
- 12. Patient Confidentiality:
 - a. Records related to this research study that involve perennial information will only be accessible by the primary research committee and direct assistants. Records will be stored on encrypted, password-protected computer hard drives. A 3-digit code number will be used rather than the subject's name to identify the specific data related to his/her involvement in the study. Only the research investigators will have access to the file that links personal

information to the 3-digit codes, and this file will be stored in a separate location from the actual research data.

Project Timeline:

Item	Date
Study Design; IRB submission ([name])	Spring 2016
Background Research	March 2016
Loose conceptual framework	March 2016
Presentation	April 2, 2016
Protocol	May 16, 2016
IRB approval	May 2016
Select study population	August 2016
Clinical Trial	November 2016

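### The primary three-way ANOVA leaves its terms, its vibration contrast and its Bonferroni family undefined in a design with one empty vibration-by-schedule cell

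*Combined protocol and SAP*

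**What the plan says.** Methods 11.b sets the primary analysis: "Our primary statistical method will be a three-way repeated measurement ANOVA, with the main effects being: vibration, aligner schedule, and time". It then leaves attribution to a later step: "the post hoc comparison will determine which specific variables are involved". Methods 11.a adds that "we will compare the five time points within each group as well as the three groups across each time point".

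Methods 1 lists the arms as "Standard Invisalign therapy (G1-control), Accelerated Invisalign therapy + vibration (G2) and Accelerated Invisalign therapy without vibration (G3"). Methods 8 confirms that the only standard-schedule arm has no vibration: "Control Group (G1): 14 patients, standard Invisalign therapy with 2 week aligner schedule". Methods 3 says of the accelerated arms: "The only difference between the intervention groups will be the use of vibration (G2 with vibration vs G3 without vibration"). That describes the design; it does not name a test.

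On multiplicity, the Abstract gives "3 way repeated ANOVA as well as a post hoc comparison with Bonferri correction", and Methods 5 says "P values less than .05 will be considered statistically significant in the overall test". The number of comparisons to be corrected for is not given anywhere.

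**The concern.** The Abstract asks whether vibration or the faster aligner schedule is responsible for quicker tooth movement. Only G2 against G3 isolates vibration, and only G3 against G1 isolates schedule. The primary method is instead worded in terms of two factors that the arms do not fully cross. The analyst would have to decide, possibly after seeing data, whether an interaction is fitted, how vibration is adjusted, whether vibration by time is included, which contrast and time point answer the question, and how many comparisons share the .05.

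A second weakness lies in the same sentence of the plan. A between-group main effect in a repeated-measures ANOVA compares means over all five time points. For outcomes analysed as levels (Little's Index, biomarkers, visit pain scores), one of the five is T0, where no treatment effect can exist. Baseline differences between patients also stay in the error term. In a trial this small, that costs power.

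**Working it through.** **1. The plan's own figure.** Methods 3 claims more than 0.8 power with 7 per group under Bonferroni. Inputs there are .04 against .28 mm/day, SD .1. With three comparisons (assumed; alpha .05/3 = .0167, two-sided t-test), power for a difference of .24 is 0.94, so the claim reproduces for accelerated against standard. G2 and G3 are given the same expected rate, so the plan states no target difference for the vibration contrast.

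**2. What can be estimated.** Code each arm as (vibration, schedule): G1 = (0,0), G2 = (1,1), G3 = (0,1).
- Full factorial, columns [1, v, s, v×s]: rank 3 of 4. With five time points it is 15 of 20. The interaction, vibration averaged over schedules and schedule averaged over vibration are not estimable. G2 minus G3 and G3 minus G1 are.
- Additive, columns [1, v, s]: rank 3 of 3. With time (v×time and s×time included) it is 15 of 15. The vibration coefficient has weights (0, 1, -1) on (G1, G2, G3), exactly G2 minus G3. The schedule coefficient is exactly G3 minus G1.

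**3. Cost of an unsized Bonferroni family.** One rate per patient, SD .1 (from Methods 3, taken as mm/day), standard error .1 × √(2/n), 3n - 3 degrees of freedom, two-sided alpha .05/k, 80% power by noncentral t.

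| Family (k) | 7 per arm | 14 per arm |
|---|---|---|
| Two named contrasts (2) | .177 | .120 |
| Three arm pairs (3) | .188 | .127 |
| Three pairs at T1-T4 (12) | .224 | .148 |
| Three pairs at T0-T4 (15) | .230 | .151 |

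Going from 2 to 15 raises the detectable G2-G3 difference by .230/.177 - 1 = 30% at 7 per arm and .151/.120 - 1 = 26% at 14. Counting the within-group time comparisons in 11.a would enlarge the family further.

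**4. Averaging over T0, level outcomes.** Assumptions, none from the plan: G2-G3 effect 0.8 SD, equal correlation r of .5 or .8 between visits, 14 per arm, alpha .05 unadjusted, SD 1. The standard error is √(2V/14).
- Five-point main effect: V = (1 + 4r)/5 = .60 or .84. An effect constant from T1 averages .8 × 4/5 = .64. The ratio to the standard error is .64/.293 = 2.19 or .64/.346 = 1.85. Power is 57% or 44%.
- T4 alone, unadjusted, as in 11.a: V = 1, ratio .8/.378 = 2.12. Power is about 54%.
- T4 with T0 as covariate: V = 1 - r² = .75 or .36. Simulated power (20,000 trials) is 65% or 93%.
- T1-T4 average with T0 as covariate: V = (1 + 3r)/4 - r² = .375 or .21. Simulated power is 91% or 99%.

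If the effect instead grows to 0.8 SD at T4, the five-point average depends on its shape:
- Linear in days (4, 14, 42, 84): .8 × (4 + 14 + 42 + 84)/84/5 = .274, power about 15% or 12%.
- Linear by visit: .8 × (.25 + .5 + .75 + 1)/5 = .40, power about 26% or 20%.

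The T4 powers keep their values (about 54% unadjusted; 65% or 93% adjusted), because the T4 effect is the same.

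**5. Where step 4 does not apply.** A rate has no T0 value. Displacement from T0 is zero for everyone at T0, so the five-point mean is 4/5 of the T1-T4 mean. Effect and standard error shrink by the same factor, and the between-group test is unchanged.

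**The case against.** The plan names main effects only. Read literally, the model is additive, has full rank and gives G2 minus G3 as its vibration effect. The three-group comparison in 11.a already contains that pair, Methods 3 says the two arms differ only in vibration, and a Bonferroni correction is announced. For the between-arm part, a three-level arm factor is only a reparameterisation of the additive model. This stands, and it limits the point to specification. It does not close it: the plan never says the model is additive, three-way ANOVA usually means the full factorial, and a literal main-effects model has no term for a vibration effect that builds over time. 11.a gives no pair or time point priority.

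Two stronger readings are tempting. A reader might infer that the primary model cannot be fitted; that is true of the full factorial but not of the terms as named. A reader might also infer that the schedule effect will be credited to vibration. That would require testing vibration without adjustment for schedule, and the plan names both factors and describes no such test.

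On baseline, the T4 comparison in 11.a already has about 54% power under the same assumptions. A vibration-by-time term, if fitted, would have 53% to 93% for a constant effect and 47% to 89% for one linear in days. The low figures therefore belong to the named main effects, not to everything the plan mentions. Rate of tooth movement, the only outcome powered, is not affected.

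Finally, the project timeline puts the thesis defence and manuscript in March and April 2018, before the document date of 08/01/2018. A choice made before analysis may no longer be possible; the documents do not say.

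**Conclusion.** The point holds as a gap in specification that should be fixed; it is not a demonstrated bias. The model terms, the vibration contrast and the Bonferroni family are open. The open family alone moves the detectable G2-G3 rate difference between .177 and .230 mm/day at 7 per arm, or .120 and .151 at 14, if the plan's SD of .1 holds at the time point tested. The design supports a vibration conclusion under the accelerated schedule only.

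For level outcomes, baseline adjustment is clearly better than the named main effects. At T4 the fair comparison with the existing plan is about 54% against 65% to 93%. These powers rest on the assumed effect and correlations, and the gain needs a baseline that correlates with later values, which a near-zero starting pain score may not do.

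**What to change.** In Methods 11.b:
- Replace the vibration and schedule factors with one three-level arm factor. Fit arm, time (T1-T4) and arm by time, with the T0 value as covariate for level outcomes.
- Name G2 minus G3 (vibration, under the accelerated schedule only) and G3 minus G1 (schedule) as the two primary contrasts, at one stated time point or for the T1-T4 average. Apply Bonferroni at .025 each.
- Label all other between-group and within-group comparisons as secondary.
- If outcome data have already been examined by arm, say so and date the choice.

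If the ANOVA is kept, the minimum is to state that it is additive in vibration and schedule, that vibration and vibration by time are tested adjusted for schedule, and how many comparisons the correction covers.

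The cost is wording only: the same data and standard software. Other pairwise and within-group comparisons lose primary status, and the covariate uses one degree of freedom.

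### Section 11b names only time-averaged main effects over five visits that include an untreated T0, and specifies no test of the rate of tooth movement

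*Combined protocol and SAP*

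**What the plan says.** The Specific Aims concern the effect of vibration "on the rate of orthodontic tooth movement, activation of gingival crevicular fluid inflammation biomarkers and patient discomfort". Section 3 (Power Analysis) is also in rate units: "The expected rate of tooth movement for G1 will be .04mm/day (.25mm/week or .5mm/2 weeks".

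The analysis is in section 11. Part (b) states: "Our primary statistical method will be a three-way repeated measurement ANOVA, with the main effects being: vibration, aligner schedule, and time". Part (a) adds that "we will compare the five time points within each group as well as the three groups across each time point". The abstract describes "a 3 way repeated ANOVA as well as a post hoc comparison with Bonferri correction". Sections 10 and 11 do not list rate as an outcome. Section 10 lists Little's Index, rotations and translations, biomarkers by ELISA, and a pain scale.

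The five time points are "TO (baseline), T1 (4 days), T2 (14 days), T3 (6 weeks) and T4 (12 weeks". In the Clinical Trial Protocol section, the baseline scan is taken at visit 3: "Treatment Plan Presentation (Experimental Baseline), 60 days post visit #1". Aligner 1 and the vibration device are handed over at visit 4, 120 days after visit 1. The schedules first diverge at visit 5, the T1 visit: "Deliver aligners 2-4 to accelerate Invisalign groups and aligner schedule instructions".

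**The concern.** In a repeated-measures ANOVA, the main effect of vibration or schedule compares arms on each patient's mean over every level of time. The result is an average level, not a rate. Where treatment starts after the first time point, the effect on an outcome that builds up over time lies in the treatment-by-time contrast, which 11b does not name.

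Two things are at stake. The reported effect may be smaller than the effect after treatment starts, because visits with no possible effect are averaged in. For outcomes measured as levels, differences between patients at baseline also stay in the error term, although the T0 value could remove them. With 7 evaluable patients per group planned, there is little room for that loss.

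**Working it through.** **1. The plan's own figure.** Inputs from section 3: 7 per group, 0.04 versus 0.28 mm/day, SD 0.1 (unit not stated, taken as mm/day). Assumed: two-sided, Bonferroni for three comparisons.
- Noncentrality = 0.24 / (0.1 × √(2/7)) = 4.49 on 12 df. At alpha 0.05/3, power is 0.94, so the claim of more than 0.8 is reproduced for accelerated versus standard.
- This is a test of rate, with one value per patient. Section 11 does not specify such a test.
- G2 and G3 have the same planned rate, so power for vibration equals alpha under any analysis.
- Separately, 0.28 mm/day does not match its own bracket (0.5/4 = 0.125); those figures must be reconciled.

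**2. Where an effect is possible.** At the T0 scan no arm has been treated. At T1, G1 and G3 have both worn only aligner 1. A vibration effect is therefore possible at four of the five time points and a schedule effect at three.

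**3. Size of the averaged estimate.** Nominal days are 0, 4, 14, 42 and 84.
- Five-point mean: 144/5 = 28.8 days. T1–T4 mean: 144/4 = 36.0 days.
- Under linear movement the main effect is 28.8 times the rate difference with T0 and 36.0 times without it. The ratio is 0.80.
- A constant schedule effect that begins after T1 is multiplied by 3/5.

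**4. Displacement from T0.** Here T0 is zero for everyone, so the effect and its SD shrink together. In a simulation (20,000 runs, 7 per group, section 3 rates and SD, alpha 0.05/3, assumed error SD 0.2 mm), power was 0.94 for the five-point mean, the four-point mean and the slope.

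**5. A level with baseline spread.** The same simulation on raw scores, with assumed baseline SDs:

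| Baseline SD (mm) | Five-point mean | T1–T4 mean | Slope |
|---|---|---|---|
| 1.5 | 0.87 | 0.89 | 0.94 |
| 3 | 0.64 | 0.74 | 0.94 |
| 6 | 0.25 | 0.36 | 0.94 |

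A unit-free version for Little's Index assumes 10 per arm, a true standardised difference of 1.0 in T0-to-T4 change and two-sided alpha 0.05. Let k be baseline SD over SD of change, r the correlation of baseline with change, and m = 28.8/84 = 0.343. The standardised main effect is m / √(k² + m² + 2rkm). Adjusting the change for T0 gives 1/√(1 − r²).

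| k | Main effect, r = 0 | Main effect, r = −0.7 |
|---|---|---|
| 0.25 | 0.40 | 0.84 |
| 0.5 | 0.22 | 0.53 |
| 1 | 0.11 | 0.15 |

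The unadjusted change has power 0.56 throughout. The T0-adjusted change has 0.56 at r = 0 and 0.84 at r = −0.7.

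**6. Biomarkers.** Assumed: constant effect d = 0.8 from T1, equal correlation ρ = 0.5, 10 per arm.
- Five-point mean: 0.8 / √((1+4ρ)/5) = 1.033 per unit of d; power 0.42.
- T1–T4 mean: 1 / √((1+3ρ)/4) = 1.265.
- T1–T4 mean adjusted for T0: 1 / √((1+3ρ)/4 − ρ²) = 1.633; power 0.79.
- Sample-size factors: (1.265/1.033)² = 1.5 for dropping T0 and (1.633/1.265)² = 1.67 for adjustment, together 2.5. The combined factor is 1.8 at ρ = 0.3 and 4.2 at ρ = 0.7.

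**7. Calendar.** Visits 7 and 8 fall 176 and 218 days after visit 1, which is 56 and 98 days after visit 4. That conflicts with 6 and 12 weeks (42 and 84 days). The 0.80 ratio does not depend on this: (0+4+14+56+98)/5 = 34.4 against 172/4 = 43.0.

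**The case against.** A reader might infer that rate is never tested. The documents do not go that far. Section 11a compares the groups at each time point, 11b adds a post hoc step, and listing factors as main effects does not exclude interactions with time. What stands is that none of these is named as the treatment test, and a visit-by-visit comparison of a raw score is still not a rate.

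A reader might also infer that the test is always weakened. If superimposed models are scored as displacement from T0, it is not. Under constant rates the main effect is then zero exactly when the rate difference is zero, so a null result would be informative. The plan does not say which scale enters the ANOVA.

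It is tempting to say T0 cuts the estimate to 34% of the week-12 difference (28.8/84). Without T0 it would still be 36/84 = 43%. The remaining gap comes from setting an average against its last visit. Similarly, only 1.5 of the 2.5-fold sample-size factor for biomarkers is due to T0.

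The power figures rest on SDs and correlations that the documents do not give. If baseline and change are strongly negatively correlated, the main effect at k = 0.25 beats the unadjusted change (0.84 against 0.56). Against the T0-adjusted change it only draws level there (0.84) and is behind at larger k (0.53 and 0.15).

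**Conclusion.** The point holds as one of specification and efficiency. The only treatment terms named as primary are time-averaged main effects over five time points that include an untreated T0, and no test of the powered quantity is specified. Under linear movement T0 multiplies the averaged estimate by 0.80; for schedule, a constant later effect shrinks to 3/5. There is no power loss for displacement from T0. For Little's Index and biomarkers the loss ranges from none to severe, depending on baseline spread and correlations that had to be assumed. For biomarkers, an untreated T0 also assumes that the visit 4 sample is taken before aligner 1 and the device are used. Randomisation keeps the averaged comparison valid, so this is a should-fix.

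**What to change.** In section 11b:

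- Define the dependent variable for each outcome, take T0 out of the time factor, and use it as the baseline.
- For tooth movement, test G2 minus G3 (vibration) and G3 minus G1 (schedule) on a per-patient slope or on T0-to-T4 change per day of active treatment. Adjust Little's Index for its T0 value.
- Count days from delivery of aligner 1 at visit 4. Counting from the visit 3 scan would include 120 − 60 = 60 untreated days in a scan-to-scan interval of 218 − 60 = 158.
- For biomarkers, test the post-baseline mean adjusted for T0: T1–T4 for vibration, T2–T4 for schedule. Treat pain likewise, using post-baseline diary or visit scores adjusted for the pre-treatment score.
- State that time-averaged main effects are not the treatment test.
- Reconcile the visit days for T3 and T4 with 6 and 12 weeks.

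The cost is wording and one degree of freedom for the covariate; every value is already scheduled. A slope keeps the intermediate scans in the test, whereas the T0-to-T4 change makes them supportive.

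### The plan's only analytic provision for heavy drop-out is an optional survival analysis, although no outcome is a time to event and an analysis of all available scans would keep more information

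*Combined protocol and SAP*

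**What the plan says.** Section 11(b) (Statistical Analysis) sets the main method: "Our primary statistical method will be a three-way repeated measurement ANOVA, with the main effects being: vibration, aligner schedule, and time". It does not say how missed visits are handled. Section 11(c) then offers one further method, which "could be a survival analysis which would be more favorable in the case our study experiences a high volume of drop-outs during treatment". It gives no event, threshold, time origin, censoring rule, survival model or definition of heavy drop-out.

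The Study Design section states the aims as effects "on the efficiency of tooth movement, on the activation of gingival crevicular fluid biomarkers and on patient discomfort". Section 10 (Data Analysis) lists the measures: "Little's Index", six-degree-of-freedom movement, 3D surface mapping, ELISA levels and the Faces Pain Scale. Scans are taken at baseline, 4 days, 14 days, 6 weeks and 12 weeks.

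The Adverse Events section says that patients with an event such as "uncontrolled pain or allergy will be disenrolled from the study and allowed to continue Invisalign therapy using the standard two-week aligner schedule". Non-compliant patients are also disenrolled. The Hypothesis section expects vibration to reduce pain. The Power Analysis section recruits 42 patients, aims for 21, and cites 30% drop-out.

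**The concern.** Section 11(c) expresses a preference: with many drop-outs, survival analysis is the better choice. The trial's data do not support it, for three reasons.

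- The outcomes are repeated continuous or ordinal measures. An event would have to be created by cutting tooth movement at a level the plan does not state, so the level would be chosen after the fact.
- The event could be observed only at one of four post-baseline visits. Most of what a scan series says about how far the teeth moved would be discarded.
- Standard survival methods assume that censoring is unrelated to the outcome. The protocol itself removes patients for uncontrolled pain and non-compliance. Pain is a study outcome expected to differ by arm, and non-compliance plausibly affects movement.

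At stake is the comparison that isolates vibration, G2 versus G3. Any true difference there may be modest, and little information can be spared.

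**Working it through.** **1. The plan's own power figure.** Inputs from the Power Analysis section: G1 0.04 mm/day, G2 and G3 0.28 mm/day, SD 0.1, 7 per arm. The difference is 0.28 − 0.04 = 0.24, or 0.24/0.1 = 2.4 SD. Two-sided t-test: noncentrality = 0.24/(0.1 × √(2/7)) = 4.49 on 12 df. Power is 0.984 at alpha 0.05 and 0.938 at 0.05/3 = 0.0167. The stated figure of more than 0.8 is reproduced for G1 against either accelerated arm. For G2 versus G3 the assumed difference is 0.28 − 0.28 = 0, so the plan states no power for vibration.

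**2. Drop-out arithmetic.** 42 × 0.70 = 29.4, so about 29 patients remain at the cited 30%. The target of 21 is reached only at 1 − 21/42 = 50% loss. Both rates are examined below.

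**3. Power by simulation.** Common settings: two arms of 14, scans at days 4, 14, 42 and 84, random drop-out after T1, T2 or T3, alpha 0.05 two-sided. Three analyses are compared: per-patient slope from all available scans (standing in for a mixed model), 12-week completers only, and log-rank on the first visit at or above a threshold. Trajectory, noise and thresholds are assumptions, because the documents give none.

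- Setting A: linear movement, mean 0.125 mm/day, between-patient SD 30% of the mean, scan error 0.2 mm, thresholds 3, 5, 8 and 10 mm.
- Setting B: progress follows the square root of time, between-patient SD 0.3 of the mean, visit noise 0.045, thresholds 0.75 and 1.0 of mean 12-week progress.

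| Setting | Effect | Drop-out | All scans | Completers | Log-rank |
|---|---|---|---|---|---|
| A | 1.0 SD | 30% | 66% | not tabulated | 11–38% |
| A | 1.2 SD | 30% | 81% | 69% | 18–50% |
| B | 0.85 SD | 30% | 56–57% | 40–41% | 37–40% |
| B | 0.85 SD | 50% | 53–54% | 29% | 29–30% |
| B | 1.2 SD | 30% | 84–85% | 69–70% | 61–63% |
| B | 1.2 SD | 50% | 84% | 52% | 53–54% |
| B | 2.4 SD | 30% | 100% | 100% | 99% |
| B | 2.4 SD | 50% | 100% | 96% | 97–98% |

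Against all scans, the log-rank loss at 1.2 SD and 30% drop-out is at least 81 − 50 = 31 points in A and about 21 points in B (83.6 − 63.0). A wider run over both shapes, 30% to 50% drop-out and 1.0 to 1.2 SD gave 62–87% for all scans and 8–70% for log-rank; the upper ends differ by 87 − 70 = 17 points. Roughly 15 points or more is a fair summary.

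With the plan's stated rates and SD, 0.2 mm scan error and thresholds from 1 to 10 mm, log-rank reaches 99% or more at 30% drop-out. At 50% it reaches 97–99.8%, against 96% for completers.

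**4. What survival analysis could detect.** By Schoenfeld's formula, the hazard ratio for 80% power is exp[(z₁₋α/₂ + 0.842)/√(events/4)]. If all 28 patients in two arms had an event: exp(2.802/2.646) = 2.9 at alpha 0.05, and 3.4 at 0.0167. With 14 events the figures are about 4.5 and 5.6.

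**5. Informative withdrawal.** With no true arm effect, faster movers more likely to leave, and about 30 points more drop-out in one arm, the mean log-rank Z shifted by −0.25 to −0.72 against that arm. The false-positive rate was 3.5% to 9.5%, depending on threshold. The all-scan slope stayed within 0.03 SD of zero, though in a setting whose curve shape the slope model knew exactly.

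**The case against.** The strongest reply is that 11(c) is a passing remark and that the loss depends on the reviewer's inputs and comparator. Much of this stands.

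- A reader might infer that the plan has no other response to drop-out. It has one: it recruits 42 for a target of 21. Section 11(c) is the only *analytic* provision.
- A reader might infer a committed switch away from the ANOVA. The wording is optional: "One additional method for statistical analysis could be a survival analysis". Nothing withdraws 11(b).
- A reader might infer that 30% drop-out would trigger it. The trigger is undefined, and 30% still leaves about 29 patients, above target.
- A reader might infer that two methods mean a free choice of the smaller p-value. In Setting A with no true effect, that practice raises the false-positive rate from about 5% to between 6% and 9%, but the plan does not say the team would do it.
- The all-scan comparator is not in the plan. Against completers only, the log-rank loss ranges from clear (Setting A, 18–50% versus 69%) to none (Setting B at 50% drop-out).
- Informative withdrawal also threatens the ANOVA, and a mixed model assumes missingness at random.

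What does not stand is the defence of the stated preference. Matching a completers-only analysis in some settings does not make survival analysis the better choice when every scan could be used. The 2.4 SD effect is a schedule effect and gives no reassurance about vibration.

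**Conclusion.** The concern holds in a limited form. Section 11(c) prefers a method that cannot be carried out as written, does not suit the outcomes, and rests on a doubtful censoring assumption. Against an analysis of all available scans it costs roughly 15 points of power or more at 1.0 to 1.2 SD. That size rests on the assumed trajectory, noise, thresholds and random drop-out. The loss is negligible at the plan's 2.4 SD schedule effect, so it matters mainly for G2 versus G3.

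Two stronger readings are not supported. One is that survival analysis would lose power whatever the effect or comparator; the table contradicts it. The other is that most withdrawals will be informative. The protocol names disenrolment reasons that may be related to outcome and arm, but it does not break down the 30% by reason, so the amount of bias cannot be estimated from the documents.

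**What to change.** Delete 11(c). State instead that, whatever the drop-out rate, tooth movement is analysed with a likelihood-based mixed model for repeated measures, with arm, time, arm-by-time and baseline value, using every scan obtained.

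Add one missing-not-at-random sensitivity analysis in which values after withdrawal for pain or non-compliance are imputed under a less favourable assumption fixed in advance. This is needed because the mixed model does not by itself remove bias from informative withdrawal. If retention is of interest, show time to disenrolment by arm as a descriptive display only.

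The cost is protocol and SAP wording and a little more analysis work, with no extra patients or visits. The downside is giving up an optional fallback.
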